Random assignment. Cluster randomization will be used to assign students according to their residential affiliation to the **immediate intervention condition** or the **waitlist condition** (i.e., delayed access). This randomization plan has been discussed with the Dean of Students Office and was preferred over a fully randomized assignment of students. Although cluster randomization can introduce statistical confounds for analyzing intervention outcomes at the individual participant level, they can be preferred: (a) to avoid intervention “contamination” effects (e.g., if participants in both conditions can regularly interact and thus might exchange health-related knowledge), and (b) if it allows the intervention to be delivered as it would be in real practice (Cook, Delong, Murray, Vollmer, & Heagerty, 2016). Moreover, the benefits of cluster randomization by residential house/dorm affiliation for this trial are crucial for the social aspects of the StriveWeekly program. For example, students will know who else is concurrently participating in the program (e.g., any of their friends in X, Y, Z house), allowing for peer-to-peer engagement. Also, this will allow for easier coordination of any optional complementary programming by residential staff at each house/dorm. A randomizer was already used to assign half the freshmen and upperclassman residential buildings to each condition:

Immediate StriveWeekly Access	Delayed StriveWeekly Access
Houses: Adams, Cabot, Currier, Dudley, Mather, Quincy, Winthrop	Houses: Dunster, Eliot, Kirkland, Leverett, Lowell, Pforzheimer
Freshmen: Ivy Yard, Elm Yard	Freshmen: Crimson Yard, Oak Yard, Maple Yard

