The below sections contain additional questions depending on the type of research that you are conducting and is meant to supplement the study overview. Please complete each section, as applicable.

SURVEYS/ QUESTIONNAIRES/PSYCHOMETRIC TESTING

Skip this section if not applicable.

5.2 List the names of all surveys/questionnaires/psychometric tests to be used in this study and a description of any that are not standard/formally named (such as study-specific questionnaires).

See full details in uploaded measure battery.

1. **Self-report demographic questionnaire** (age, gender, ethnicity, academic year).
2. **Branding feedback.** There will be a few questions about if students would have been more or less likely to sign-up for the program had it been under a different name (e.g. "The Happiness Challenge")
3. **Treatment Motivation Questionnaire (TMQ).** Questions from the Treatment Motivation Questionnaire (Ryan, Plant, & O'Malley, 1995) have been minimally adapted to apply to an online mental health promotion program instead of a treatment. Questions from the help-

seeking subscale were removed. This 20-question measure will assess participants' reasons for signing up and expectations for completing the program. The TMQ has significant predicted intervention completion in other research studies, for example in-person alcohol treatment (Ryan et al., 1995) and online trauma treatment (Alfonsson et al., 2016).

4. **Depression Anxiety and Stress Scale.** The primary symptom outcome measure will be the 21-item version of the Depression Anxiety and Stress Scale (DASS-21), which assesses self-reported symptoms related to depression, anxiety, and stress. The DASS-21 has demonstrated high internal consistency (.83 - .90) and good construct validity in university student samples (Norton, 2007). Note: There are no questions related to suicidality.
5. **Perceived Stress Scale.** This measure is a 10-item scale that is the most widely used psychological instrument for measuring the perception of stress. It is a measure of the degree to which situations in one's life are appraised as stressful. Items were designed to tap how unpredictable, uncontrollable, and overloaded respondents find their lives.

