6. **Self-reported service use.** Students will be asked to indicate past and current use of health-related services on- and off-campus using a checklist of common resources/services (e.g., off-campus therapy, psychiatry at HUHS, etc.) as well as a write-in "other" option.
7. **Technology use.** Students will be asked to indicate the types of devices they use, their internet access, health data settings, etc.
8. **Checklists / weekly hour estimates of extracurriculars and regular behaviors.** See uploaded battery.
9. **Life Events Checklist.** Items combined from the following standardized measures: Life Events Scale for Children, Adolescent Perceived Events Scale, and Life Events Checklist for DSM-5 (LEC-5). Some original items added, including COVID-19-related items.
10. **General Belongingness Scale.** A standardized 12-item measure to assess a sense of general belongingness, which has been previously validated in student samples.

Pilot / Posttest / Follow-Up Survey Only

11. **Program satisfaction.** The posttest and follow-up surveys will include questions about experiences with the program for the respective group that just completed the intervention. This 5-item measure is adapted from the Client Satisfaction Questionnaire (Larsen, Attkisson, Hargreaves, & Nguyen, 1979), which has been found to be an appropriate measure of satisfaction with high internal consistency and concurrent validity across a broad range of intervention contexts (e.g., children's outpatient mental health services, Copeland, Koeske, & Greeno, 2004; adult outpatient setting, De Wilde & Hendriks, 2005; adult residential treatment setting, Kelly et al., 2018).
12. **Module preferences.** Students will be asked to rank the modules in order of the most to least favorite.
13. **Open-ended feedback.** There will be an open text field for participants to write any feedback they had about their experience.
14. **Tech-based intervention barrier scale.** A 10-item self-report scale to assess barriers experienced by users of tech-based interventions (Ramos, Hammons, Chavira, & Rith-Najarian, 2019)

Follow-Up Interview

15. **Study-specific semi-structured interview.** A subsample of students will be asked a series of open-ended questions to gather feedback about their experience with StriveWeekly and invite proposed adaptions to improve acceptability, feasibility, and engagement for a targeted sample of students endorsing identification with the LGBTQ+ community.

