7. CHARACTERISTICS OF THE STUDY POPULATION

7.1 Indicate the estimated number of participants, by subgroup if applicable. If it is not possible to estimate the number of participants (e.g., open online survey), please indicate that it is not possible and provide an explanation of why it is not possible.

It is not possible to estimate how many participants will enroll, as it will be open to all Harvard undergraduate students who are interested in enrolling. The maximum sample size therefore cannot exceed the size of the undergraduate student body (~6000). By contrast, the randomized controlled trial at UCLA enrolled 1600+ students from an entire student body of 40,000+. This programming was not centrally sponsored by an equivalent to the Dean of Students Office though, so we expect the relative enrollment rate to be higher by percentage of enrolling students relative to total student body. The secondary analyses on a subset of survey data is estimated to include approx. 125 students endorsing identification with the LGBTQ+ community. We expect to conduct follow up interviews with approximately 20 to 30 participants to achieve saturation.

7.2 Describe the criteria for enrollment – Will you be limiting your enrollment to a certain age range, gender, people with certain health conditions, etc.? Please also describe any criteria that will exclude people from enrollment.

We will recruit undergraduate students who are currently enrolled as fulltime students at Harvard as of the time of recruitment. There are no *a priori* exclusion criteria. *Post hoc* exclusion procedures will remove students with invalid data reporting (e.g., straight-lined responses to surveys, high inconsistency in responses to cross-validation item pairs selected based on content similarity). Additionally, inclusion criteria for secondary analyses assessing outcomes among sexual and gender minority subgroups will include endorsement of belonging to the LGBTQ+ community. Students eligible to participate in the follow up interviews will be those who (a) used the StriveWeekly platform at least

once, (b) completed all study surveys, and (c) either identify as LGBTQ+ or want to provide feedback about program inclusivity for this community.

7.3 Are there any potential vulnerable populations or individuals proposed for involvement in the research? (check all that apply)

- Children
- Wards of the State
- Prisoners/Detainees
- Pregnant Women
- Adults not Competent to Consent

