12.16 How will the consent forms be collected and stored?

- Paper
- Electronic

12.17 Will subject contact information or other individually identifiable subject information be stored in the data set?

- No
- Yes

12.18 Explain where the research data will be stored while the study is active (e.g., personal laptop, thumb drive, departmental computer server, office file cabinet, etc.).

During the study, documentation of identifying information within consent forms and participant ID key will be stored on Harvard Qualtrics, which will be accessible only by the PI of this study. The Harvard Qualtrics site login requires HarvardKey dual authentication. The electronic consent forms will be stored separately from survey responses. The Harvard Qualtrics surveys will be configured to use an auto-generated participant ID, matched to email addresses in the separate ID key.

The StriveWeekly Platform User Database for the Harvard-hosted instance will be stored on a HUIT-managed AWS EC2 instance. HUIT will provide [name] with access to this database.

Once all data collection is complete, [name] (StriveWeekly owner) will download the StriveWeekly user database onto a personal work laptop (due to remote work set-up) while logged into Harvard's network via Cisco VPN. At the same time, [name] in her role as the Harvard-affiliated study PI will download all the survey datasets from Qualtrics. Once all these datasets are downloaded as Excel files, email addresses in the StriveWeekly user database will be used to link all assigned participant IDs per the Qualtrics ID key. The datasets (platform database and Qualtrics surveys) will then all be merged into a password-protected master dataset using these participant IDs. This master file will thus have no identifying data within it. The password for the master data will be known only by the PI, and anyone listed in the IRB for the corresponding study (currently or in the

future). All downloaded files will be permanently deleted from the laptop, and the master dataset will be saved within the PI's Harvard O365 OneDrive. [name] (Graduate Assistant) and [name] (Graduate Assistant) will help with management of the resulting dataset.

12.19 What will happen to the data at the conclusion of the study? (check all that apply)

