13. SHARING DATA WITH OTHERS

13.1 Will the data be released to anyone who is not on the Harvard University Area research team?

Yes

No (*skip to question #13.4*)

13.2 Other than the Harvard University Area research team, who will have access to the data?

Colleagues/Collaborators at other institutions

Transcribers/coders hired by the research team

Sponsor/Funding Agency

OpenScience or other framework (Specify: <https://osf.io/8dvjq/>)

Other (*see below*)

If "Other" please specify:

Collaborators at other institutions: While the data is being collected, [name] will be helping collect and process data via Harvard Qualtrics, the StriveWeekly platform, Harvard OneDrive, and Harvard Zoom. After the data collection is complete, [name]'s access to these services will be revoked. At that time [name] will then be provided de-identified data files. See details in 12.21 above.

OpenScience: a de-identified copy of main study variables (e.g., condition assignment, outcome measure total scores) will be uploaded to the PI's OSF profile. This copy of the dataset will contain none of the qualitative open-ended response data. In future published manuscripts, the PI will offer de-identified versions of other variables should other researchers wish to verify study results, or use study data for secondary analysis or meta-analysis research.

Other: See 5.25 and 12.18 for explanation of [name]'s external role as StriveWeekly website owner

13.3 How will the data be shared/disclosed beyond the Harvard University Area research team?

- Without any identifiers
- Coded
- With Identifiers

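### The post hoc validity screen in Protocol 7.2 removes whole students without being limited to baseline answers or blinded to arm, and these documents state no analysis that keeps them

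*Protocol*

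**What the plan says.** Protocol 7.2 excludes nobody in advance. It then states that post hoc "exclusion procedures will remove students with invalid data reporting (e.g., straight-lined responses to surveys"). The second example is marked disagreement within "cross-validation item pairs selected based on content similarity". Both are examples rather than a closed list, and neither has a cut-off. The text speaks of surveys without naming a wave, and Protocol 5.1 (Data collection) has four: baseline, posttest, 2-month and 5-month. The unit removed is the student, not the affected survey.

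Allocation came first. Protocol 5.1 (Random assignment) says "A randomizer was already used to assign half the freshmen and upperclassman residential buildings to each condition".

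The later surveys are not the same for everyone. Under Protocol 5.2, item 11, the posttest and follow-up surveys carry "questions about experiences with the program for the respective group that just completed the intervention".

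On data handling, Protocol 12.18 says that after data collection ends the study lead "will download all the survey datasets from Qualtrics", and adds: "The datasets (platform database and Qualtrics surveys) will then all be merged into a password-protected master dataset using these participant IDs". No section says that the screen is fixed before that point or run on a file without arm.

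The SAP's Data analysis section gives the piecewise mixed model, effect sizes, post hoc moderators and mediators, and Benjamini-Hochberg control. It mentions no validity screen, no analysis set and no analysis with the screened students retained.

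**The concern.** The comparison is protected by allocation only if the students analysed in each arm are those allocated to it, or are reduced by a process that cannot depend on the arm. A screen on answers given before the program starts comes close to meeting that condition. A screen on answers given afterwards need not, because the program can influence who answers, how they answer and which questions they see.

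The text allows the second kind of screen. It also allows a flag on a late survey to delete the valid baseline and posttest data of the same student. If removals then differed by arm in number or in kind, the primary comparison would no longer be between the groups as allocated. With no unscreened result beside it and no count of removals by arm, a reader could not tell whether that had happened.

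**Working it through.** The plan states no removal rate, sample size or bias figure for this step, so there is nothing to reproduce. The check sets the sections side by side and then gives a scale illustration.

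**Step 1: what a flag at each survey would mean** (Protocol 5.1 timeline; Protocol 5.2, items 11 to 14)

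| Survey | Position | Program-experience questions | Risk if a flag removes the whole student |
|---|---|---|---|
| Baseline | Closes 17 September; first round starts 20 September | None | Little: the answers precede program use |
| Posttest | After the immediate arm's round | Immediate arm | Removal could differ by arm |
| 2-month | Before the delayed arm's round | Arm not spelled out | Removal could differ by arm; earlier valid data lost |
| 5-month | After the delayed arm's round | Delayed arm | Removal could differ by arm; earlier valid data lost |

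Protocol 7.2 does not say which row applies.

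**Step 2: when removal shifts the result.** Let f be the share of an arm removed, and g the distance between the removed students' mean baseline-to-posttest change and their arm's mean change, in SD units. The mean of those retained moves by −f·g/(1−f). The shift in the arm contrast is the difference between the two arms' movements. This is a simple two-point contrast and does not reproduce the piecewise model. Every f and g is assumed. The only documented figure is d = 0.25, the prior trial's effect (Protocol 4.2), used as a yardstick.

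- 5% and 5%, same g: the two movements cancel; shift 0.
- 5% and 2%, same g: g × (0.05/0.95 − 0.02/0.98) = g × 0.0322. This is 0.016 SD at g = 0.5 and 0.032 SD at g = 1.0, or 6% and 13% of 0.25.
- 10% and 5%, same g: g × (0.10/0.90 − 0.05/0.95) = g × 0.0585. This is 0.029 SD at g = 0.5 and 0.058 SD at g = 1.0, or 12% and 23% of 0.25.

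The sign depends on whether removed students lie above or below their arm's mean. Equal rates would also shift the contrast if a different kind of student were removed in each arm.

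**Step 3: what keeping careless responders costs.** Suppose a share p in both arms answers carelessly and shows no effect, with answers of k times the SD and a mean m SD away. The diluted effect is 0.25(1−p)/√[(1−p) + p·k² + p(1−p)·m²].

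- k = 1, m = 0: 0.25 × 0.95 = 0.238 at p = 5%; 0.25 × 0.90 = 0.225 at p = 10%.
- k = 1.5, m = 1: 0.2375/√1.11 = 0.225 at p = 5%; 0.225/√1.215 = 0.204 at p = 10%.

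These inputs are also assumed. They show that neither the screened nor the unscreened analysis is free of cost.

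**The case against.** Screening out careless answers is ordinary practice in paid online surveys, and the protocol names two recognised kinds of careless responding. That stands, and the fix keeps a screen.

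Removal after allocation is not a fault in itself. Buildings were allocated first, so every student-level step follows allocation, consent and baseline included. That also stands: the difficulty lies only with answers given after baseline.

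Nothing says that the program-experience questions feed the screen. The item pairs could all come from scales given to both arms, and the uploaded measure battery, which is not among these documents, may list them. This is fair, so the difference in survey content is a possible route rather than a shown one. A list of pairs would still not supply cut-offs, a wave, blinding or an unscreened analysis. The SAP also describes itself as an excerpt from a 2020 proposal, so the most that can be said is that these documents state no such analysis.

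A reader might go further and infer that a symptom-free student who gives the lowest answer to all 21 DASS-21 items would be flagged, so that the screen selects on the outcome. The documents do not support this. Protocol 7.2 refers to straight-lined surveys, each survey is a battery of several measures, and neither the response options nor the direction of the DASS-21 items is given.

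**Conclusion.** The point holds as a gap that is cheap to close. Protocol 7.2 commits to removing whole students on open-ended criteria, does not confine this to baseline or blind it to arm, and has no stated counterpart analysis that keeps them. If post-baseline answers are used, the arms could lose different students.

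A reader might infer that the screen will bias the trial, or that it will be applied with knowledge of arm. Neither follows. The documents are silent on blinding, which is not evidence that it will be absent, and they do not show that removals will differ by arm. Size and direction cannot be estimated. The shifts of 0.016 to 0.058 SD above are illustrations that rest wholly on assumed removal rates and deviations; like removal in both arms gives zero. The point should be addressed, with medium confidence: the omission from these documents is clear, but its consequence is unknown.

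**What to change.** 1. Remove whole students only on baseline items common to both arms. Write down the cut-offs and item pairs, and apply them to a file without arm, house or yard, or platform data.
2. Where a later survey is flagged, set that wave to missing in a sensitivity analysis instead of deleting the student. Use only items common to both arms. This is the analysis that addresses careless posttest answers.
3. Report the primary model on all consenting students with a baseline survey, by allocated house or yard, beside the screened result. Which of the two is labelled primary is the team's choice, but it must be fixed before outcomes are compared by arm. Protocol 5.1 also leaves open whether pilot participants are dropped from the final sample; state the decision and apply it in the same way in both arms.
4. Report the number removed by arm and by reason.

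The cost is protocol and SAP wording and one or two more model runs, with no new data. Careless responders kept in the unscreened analysis may dilute the effect, for example from d = 0.25 to about 0.24 to 0.20 if 5% to 10% answer carelessly (assumed). That is a reason to show both results rather than either alone.

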4. RESEARCH PURPOSE

4.1 Provide a brief, non-technical description of the purpose of the research, including the research questions that you hope to answer.

We aim to evaluate the effectiveness of StriveWeekly in preventing symptoms of anxiety and depression within a remote campus learning environment. The use of a waitlist condition will allow us to experimentally assess if the online intervention is responsible for decreasing / preventing worsened anxiety, depression, and stress symptoms over time. Given the previously established effectiveness of StriveWeekly as a universal prevention program, we expect students in the intervention condition to experience significantly better symptoms compared to the waitlist from baseline to posttest.

Alternatively, if the remote campus learning environment and/or the broad pandemic context interferes with the acceptability or effectiveness of StriveWeekly, then we would expect to see no significant differences between the online intervention condition and waitlist condition from baseline to posttest. The results of this project are intended to contribute to generalizable, and publishable knowledge in the field.

Secondary aims include: (a) testing moderators of intervention effectiveness and (b) evaluating the intervention in terms of acceptability (e.g., feedback on program name; demographically representativeness of student user sample; satisfactory adherence and satisfaction rates). Exploratory moderation analyses across groups will help determine whether or not the intervention condition produces unique or additive effects for students with certain characteristics over and above changes demonstrated by similar students in the waitlist condition. Acceptability analyses will allow for more nuanced evaluation of StriveWeekly's effectiveness as a program, beyond its ability to facilitate symptom reduction. Secondary analyses and follow up interviews with diverse subsamples of students will help to assess generalizability of StriveWeekly outcomes, determine acceptability among underserved populations, and inform future research.

4.2 Describe the scientific background, rationale for the study, and importance of this research in adding to existing knowledge.

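### The straight-lining exclusion in Protocol 7.2 has no exception for a truthful uniform answer; if judged on the DASS-21 it could remove symptom-free students, and at post-randomisation waves unequally by arm

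*Protocol*

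**What the plan says.** Protocol section 7.2 sets no entry restriction beyond current full-time undergraduate enrolment: "There are no *a priori* exclusion criteria". It then provides that, post hoc, "exclusion procedures will remove students with invalid data reporting (e.g., straight-lined responses to surveys". The second example of invalid reporting is "high inconsistency in responses to cross-validation item pairs selected based on content similarity". The stated consequence is removal of the student, not of one response or one scale. The section does not say whether straight-lining is judged within a scale, across scales or over a whole survey. It names no wave and no cut-off, and it makes no exception for a plausible uniform answer.

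Section 5.2 makes the 21-item DASS-21 the primary symptom measure, "which assesses self-reported symptoms related to depression, anxiety, and stress". Item wording and response options are in a separately uploaded battery. Section 4.1 describes the programme by its "previously established effectiveness of StriveWeekly as a universal prevention program" and expects fewer symptoms in the intervention arm than in the waitlist arm by posttest. The SAP excerpt specifies piecewise linear mixed models. It defines no analysis set and no sensitivity analysis for these removals.

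**The concern.** On a list of symptoms, giving the same lowest answer throughout is what a careless student may do, and also what an attentive student with no symptoms should do. With no symptom threshold for entry, students of the second kind are eligible. On this instrument the indicator therefore partly measures the outcome rather than the quality of the response.

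Two things are at stake. If the rule is applied to DASS-21 data after randomisation, exclusion depends on the outcome, and the arm that does better loses more of its best results. Section 4.1 would read the absence of a significant difference as a sign that the remote or pandemic setting interfered with the programme, so a bias towards zero favours a specific substantive conclusion. If the rule is applied at baseline, it removes students without symptoms, who belong to the population that a universal prevention programme addresses.

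Fixing a threshold or blinding the person who applies the rule would not cure this. A blinded rule with a fixed threshold, applied to the DASS-21, would still catch truthful all-lowest answers.

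**Working it through.** The documents give no all-lowest rate, DASS-21 mean, SD or planned sample size, so there is no stated figure to reproduce. The one usable input is the prior-trial effect, d = 0.25 (section 4.2). Everything else below is an assumption: 21 items scored 0 to 3, all in the symptom direction; the rule applied to the posttest DASS-21; every all-zero responder removed. The calculations compare posttest means and ignore clustering and baseline adjustment.

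**Step 1. Does the item-pair check rescue the truthful responder?** It flags inconsistent answers to similar items. An all-lowest responder, truthful or careless, answers similar items identically. The check neither clears the first nor catches the second.

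**Step 2. Censored-normal total.** Let the total be max(0, μ + Z) in SD units, with Z standard normal. Then:
- zero share p = Φ(−μ)
- mean m = μΦ(μ) + φ(μ)
- variance v = (μ² + 1)Φ(μ) + μφ(μ) − m²
- after deleting zeros, mean = m/(1 − p) and variance = (v + m²)/(1 − p) − [m/(1 − p)]².

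Fix the waitlist p, and choose the intervention μ so that d = 0.25 before deletion. Worked case, waitlist p = 5%:
- Waitlist: μ = 1.645, m = 1.666, v = 0.915.
- Intervention: μ = 1.393, p = 8.2%, m = 1.430, v = 0.865.
- Before: d = (1.6657 − 1.4299)/√[(0.9152 + 0.8648)/2] = 0.2358/0.943 = 0.250.
- After: means 1.7534 and 1.5574, variances 0.8096 and 0.7434, so d = 0.1960/0.881 = 0.222.

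| Waitlist removed | Intervention removed | d after | Loss |
|---|---|---|---|
| 0.5% | 1.0% | 0.244 | 2% |
| 1% | 1.9% | 0.240 | 4% |
| 2% | 3.6% | 0.234 | 6% |
| 5% | 8.2% | 0.222 | 11% |
| 10% | 15.2% | 0.210 | 16% |

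The lower-symptom arm loses 1.5 to 2.0 times as many students. With d = 0, removals are equal and the comparison is unbiased.

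**Step 3. One-factor item model.** Factor f is N(0, 1) in the waitlist arm and N(−0.25, 1) in the intervention arm. Each item has latent value y = λf + √(1 − λ²)e + s, with e standard normal, and its score is the number of the thresholds 0, 1.0 and 1.8 that y exceeds. The shift s (0.35, 0, −0.3, −0.6) sets the waitlist mean total. With 200,000 simulated students per arm and d on the waitlist SD of the sample analysed, the percentage loss in d is:

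| Loading λ | Mean about 20 | Mean 14.6 | Mean 10.4 | Mean about 7 |
|---|---|---|---|---|
| 0.5 | 0.5 | 1.7 | 4.5 | 7.1 |
| 0.6 | 1.5 | 4.2 | 7.0 | 12.0 |
| 0.7 | 3.9 | 7.2 | 11.2 | 14.3 |
| 0.8 | 8.0 | 12.0 | 14.4 | 17.7 |

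The last digits carry simulation error. At λ = 0.7, removals (waitlist vs intervention) are 4.3% vs 6.8% at mean 14.6 and 9.1% vs 13.6% at mean 10.4. The corner cells correspond to 0.09% vs 0.18% (smallest loss) and 26.7% vs 35.3% (largest loss).

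**Step 4. Negative binomial total on 0 to 63.** With mean 10 to 20, size 1 to 2.5 and d = 0.25, zero shares run from 0.4% vs 0.6% to 9.1% vs 11.6%, yet d after deletion is 0.247 to 0.250. With size 1 the distribution above zero has the same shape moved up one point, so deleting zeros hardly changes d even though removals differ by arm.

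**The case against.** A reader might infer that the rule cannot tell the two kinds of responder apart, that it will delete symptom-free students, that more will always go from the better arm, and that about a tenth of the effect will be lost. The documents do not support that reading.

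- The criterion is invalid reporting, with straight-lining as an example, and the object is surveys rather than the DASS-21. The baseline battery also holds a 20-question motivation scale, a 10-item stress scale, a 12-item belongingness scale, checklists and hour estimates. Under a whole-survey or multi-scale rule, an all-lowest DASS-21 alone would not flag anyone.
- Whether other scales contain reverse-worded items that would expose careless responders cannot be checked, because the battery is not in these documents.
- No wave is named. Baseline precedes the intervention, so a baseline-only screen causes no treatment-driven imbalance.
- A loss of about a tenth is one scenario. Lower loadings or a higher symptom level bring it close to zero, as does the negative binomial model.
- The bias is towards no effect, so it cannot by itself manufacture a benefit.

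All of this stands, and it makes the point conditional. It does not remove it. A survey of mixed formats can hardly be straight-lined as a whole, so judging it on blocks such as the DASS-21 is a plausible way to apply the rule, and nothing in 7.2 rules that out. The text names an indicator and a consequence with no exception, which is more than missing detail.

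**Conclusion.** The point holds conditionally. As written, 7.2 does not distinguish careless from truthful uniform answers if straight-lining is judged on the DASS-21. If it is also applied after randomisation and the arms differ, more students are removed from the lower-symptom arm. The difference in means is then pulled towards zero, although in some models the standardised effect hardly moves. If applied only at baseline, the cost is a narrower analysed population and not a biased comparison.

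The size cannot be fixed from the documents. Over loadings 0.5 to 0.8 and waitlist means of about 7 to 20, the loss in d is about 1% to 18%; the censored-normal model gives 2% to 16% for all-zero shares of 0.5% to 10%; the negative binomial model gives almost none. The largest losses require more than a quarter of the waitlist arm to report nothing at all. The planned mixed model, clustering and removal of the student's other waves could change these figures. This is a modest, avoidable risk that merits a clarification. It is not a threat of a false positive.

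**What to change.** In Protocol 7.2, add that a uniform lowest response on the DASS-21, or on any scale whose items all run in one direction, is not by itself grounds for removal. Judge straight-lining only where identical answers are logically inconsistent: item sets worded in both directions, or uniform answers across several scales. In the SAP, report validity removals by arm and repeat the primary analysis with no validity exclusions.

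The cost is one sentence in the protocol, a matching line in the data-cleaning code, one table and one extra model run. The downside is that a few careless all-lowest responders stay in, and the similar-content item pairs will not catch them.
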